6.12.1 Adverse Events

A treatment emergent adverse event (TEAE) is defined as:

- Any AE that has an onset on or after the first dose of study drug through the end-of-study follow-up call (Day 11).
- Any pre-existing AE that has worsened in severity on or after the first dose through the end-of-study follow-up call (Day 11).

Relatedness of an AE to treatment is defined as Not Related, Unlikely, Possible, Probable or Certain. A treatment-related AE is defined as any AE classified as possibly, probably or certainly related to the study drug. If an AE has missing relationship it is assumed to be related to the study drug for analysis purposes.

Severity of AEs will be graded using the Division of Microbiology and Infectious Disease (DMID) Toxicity Grade November 2007 version: Grade 1 (Mild), Grade 2 (Moderate), Grade 3 (Severe), Grade 4 (Potentially Life-Threatening). Maximum grade will be assumed for an AE with missing grade.

The following tables will be presented for AEs:

- Overall incidence and number of AEs, SAEs, TEAEs leading to withdrawal.
- TEAEs by system organ class and preferred term, incidence and number of events
- Treatment-related TEAEs by system organ class and preferred term, incidence and number of events
- TEAEs by system organ class, preferred term and maximum grade, incidence
- TEAEs by system organ class, preferred term and relationship, incidence
- Listing of TEAEs Leading to Early Withdrawal (presented in the Table section of the appendices)
- Listing of Serious TEAEs (presented in the Table section of the appendices)
- Listing of Deaths (presented in the Table section of the appendices)

System organ class will be presented in descending order of overall frequency and then alphabetically. Preferred terms will be displayed in descending order of overall frequency and then alphabetically.

Where a subject reports more than one AE per system organ class and preferred term they will only be counted once for the most severe event or the most related event.

QMD Ref: Worldwide-TMP-ST-006-4.0 Effective: 12Aug2019	Governing QMD: Worldwide-SOP-ST-001
Confidentiality Statement	

This document is the property of Worldwide Clinical Trials Inc. and may not be duplicated, copied, altered or removed from company without prior approval from Worldwide Quality Assurance or in compliance with Worldwide Standard Operating Procedures.

Worldwide Clinical Trials Controlled Quality Management Document			
 WORLDWIDE CLINICAL TRIALS	Sponsor:	TB Alliance	
	Protocol Number:	TBI-223-CL-001	
STATISTICAL ANALYSIS PLAN – PHASE 1			

All AEs will be listed.

6.12.2 Laboratory Data

Descriptive statistics of the observed values and change from baseline (continuous data) will be presented by study part, period (where applicable), treatment group and visit for each hematology, serum chemistry, coagulation and urinalysis parameter. Each measurement (continuous data) will be classed as below, within, or above normal range, based on ranges supplied by the laboratory used. Shift tables in relation to the normal range from baseline to each follow-up visit will be presented.

A listing of any clinically significant laboratory measurements recorded throughout the study will be presented.

6.12.3 Vital Signs

Descriptive statistics for observed values and changes from baseline in the following vital signs will be presented by study part, period (where applicable) and treatment group at each visit:

- Systolic blood pressure (mmHg)
- Diastolic blood pressure (mmHg)
- Pulse rate (bpm)
- Respiration rate (breath/min)
- Body temperature (degrees Celsius)
- Pulse oximetry (%)

All vital sign data will be listed.

6.12.4 Electrocardiogram Data

Descriptive statistics for observed values and changes from baseline in the following ECG variables will be tabulated by study part, period (where applicable) and treatment group at each post-baseline assessment:

- Heart rate (bpm)
- PR interval (ms)
- RR interval (ms)
- QRS complex (ms)
- QT interval (ms)

QMD Ref: Worldwide-TMP-ST-006-4.0 Effective: 12Aug2019	Governing QMD: Worldwide-SOP-ST-001
Confidentiality Statement	

This document is the property of Worldwide Clinical Trials Inc. and may not be duplicated, copied, altered or removed from company without prior approval from Worldwide Quality Assurance or in compliance with Worldwide Standard Operating Procedures.

Worldwide Clinical Trials Controlled Quality Management Document			
 WORLDWIDE CLINICAL TRIALS	Sponsor:	TB Alliance	
	Protocol Number:	TBI-223-CL-001	
STATISTICAL ANALYSIS PLAN – PHASE 1			

- QTc interval (ms)
- QTc interval (ms) [Bazett's formula - QTcB]
- QTc interval (ms) [Fridericia's formula - QTcF]

Shift tables in relation to the overall interpretation (Normal, Abnormal NCS, and Abnormal CS) from baseline to each post-baseline assessment will be presented. All ECG data, including details of any abnormalities, will be listed.

6.12.5 Cardiac Telemetry (Holter) Data

Data relating to the collection of cardiac telemetry (Holter) data will be listed. Timings of 12-lead ECGs extracted from the continuous Holter recording will be collected on the eCRF but will not be listed for this study.

6.12.6 Physical Examination

Shift tables for the observed status of each of the body systems (Normal, Abnormal NCS, and Abnormal CS) will be tabulated by study part, period (where applicable) and treatment group at each post-baseline assessment. All data, including details of clinically significant findings will be listed.

6.12.7 Neurological Examination

Shift tables for the observed status of each neurological aspect (Normal, Abnormal NCS, and Abnormal CS) will be tabulated by study part, period (where applicable) and treatment group at each post-baseline assessment. All data, including details of clinically significant findings will be listed.

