### **3.2 Stopping Rules for Cohorts**

If any of the cohort stopping rules are met, cohort dosing must be stopped until review of the data by the Sponsor and the Investigator.

Rules for stopping dosing of a cohort include the following:

1. Two or more subjects experience drug-related SAEs;
2. Two or more subjects experience grade 2 or higher (per DMID toxicity table; Appendix 3) central nervous system (CNS) AEs considered related to drug.
3. Two or more subjects develop drug-related QTcF prolongation greater than or equal to 500 msec or a change from baseline greater than 60 msec, after completing repeat testing.
4. Two or more subjects experience drug-related Grade 3 or Grade 4 cardiac rhythm cardiac disturbances.

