6.2.8 Unscheduled Visits

Only scheduled post-baseline assessments will be tabulated. Post-baseline repeat/unscheduled assessments will not be summarized but will be listed in the relevant appendices to the CSR.

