Placebo	TBI-223 50 mg	TBI-223 100 mg	TBI-223 300 mg	TBI-223 Capsule	TBI-223 600 mg	TBI-223 (Fasted)	TBI-223 1200 mg	TBI-223 (Fed)	TBI-223 2000 mg	TBI-223 2600 mg	Overall
---------	------------------	-------------------	-------------------	--------------------	-------------------	---------------------	--------------------	------------------	--------------------	--------------------	---------

The Placebo column will include Period 1 (Fasted) and Period 2 (Fed) events.

Placebo is not administered to subjects in the repeat cohort who will receive capsule formulation.

Overall column will include all reported events during Part 1.

Part 2 / Tablet Formulation

TBI-223 1800 mg SR-1 tablet (Fed)	TBI-223 1800 mg SR-2 tablet (Fed)	TBI-223 1800 mg SR-3 tablet (Fed)	TBI-223 2000 mg IR tablet (Fasted)	TBI-223 2000 mg IR tablet (Fed)	Overall
--	--	--	---	--	---------

Overall column will include all reported events during Part 2.

Listings will be sorted in the following order: Study part, period (where applicable), treatment group (Placebo followed by TBI-223 in ascending dose order), subject number, parameter, and visit unless otherwise stated. All data will be listed.

For clinical data, continuous variables will be summarized by the number of non-missing observations, mean, median, standard deviation, and minimum and maximum.

PK data (concentration-time data and PK parameters) will be summarized by the number of non-missing observations (n), mean, standard deviation (SD), median, minimum (min), maximum (max), and coefficient of variation (CV%), calculated as (SD/Mean)*100. In addition, the geometric mean and geometric CV%, calculated as SQRT[exp(SD² of log transformed data)-1]*100, will be reported for C_{max} and AUCs.

Categorical variables will be summarized by presenting the frequency and percent. Percentages will be based on the number of non-missing observations or the subject population unless

QMD Ref: Worldwide-TMP-ST-006-4.0 Effective: 12Aug2019	Governing QMD: Worldwide-SOP-ST-001
Confidentiality Statement	

This document is the property of Worldwide Clinical Trials Inc. and may not be duplicated, copied, altered or removed from company without prior approval from Worldwide Quality Assurance or in compliance with Worldwide Standard Operating Procedures.

Worldwide Clinical Trials Controlled Quality Management Document			
 WORLDWIDE CLINICAL TRIALS	Sponsor:	TB Alliance	
	Protocol Number:	TBI-223-CL-001	
STATISTICAL ANALYSIS PLAN – PHASE 1			

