14.3.2.2	Serious TEAEs, Listing – Safety Analysis Set	IP	
14.3.2.3	Deaths, Listing – Safety Analysis Set	IP	
14.3.3	Narratives of Deaths, Other Serious and Certain Other Significant Adverse Events		
14.3.4	Abnormal Laboratory Values		
14.3.4.1	Listing of Clinically Significant Laboratory Values – Safety Analysis Set	IP	
14.3.5	Extent of Exposure, Dosage Information, and Compliance		
	Not Applicable		
14.3.6	Vital Signs and Physical Examination		
14.3.6.1	Vital Signs, Descriptive Statistics – Safety Analysis Set	IP	
14.3.6.2	Physical Examination, Change from Baseline – Safety Analysis Set	IP	
14.3.6.3	Neurological Examination, Change from Baseline – Safety Analysis Set	IP	
14.3.7	Other Safety		
14.3.7.1	Hematology Data, Descriptive Statistics – Safety Analysis Set	IP	
14.3.7.2	Hematology Data, Normal Range Shifts – Safety Analysis Set	IP	
14.3.7.3	Serum Chemistry Data, Descriptive Statistics – Safety Analysis Set	IP	
14.3.7.4	Serum Chemistry Data, Normal Range Shifts – Safety Analysis Set	IP	
14.3.7.5	Coagulation Data, Descriptive Statistics – Safety Analysis Set	IP	
14.3.7.6	Coagulation Data, Normal Range Shifts – Safety Analysis Set	IP	
14.3.7.7	Urinalysis Data, Descriptive Statistics – Safety Analysis Set	IP	
14.3.7.8	Urinalysis Data, Normal Range Shifts – Safety Analysis Set	IP	
14.3.7.9	12-Lead ECG Data, Descriptive Statistics – Safety Analysis Set	IP	

QMD Ref: Worldwide-TMP-ST-006-4.0 Effective: 12Aug2019	Governing QMD: Worldwide-SOP-ST-001
Confidentiality Statement	
This document is the property of Worldwide Clinical Trials Inc. and may not be duplicated, copied, altered or removed from company without prior approval from Worldwide Quality Assurance or in compliance with Worldwide Standard Operating Procedures.	

Worldwide Clinical Trials Controlled Quality Management Document			
 WORLDWIDE CLINICAL TRIALS	Sponsor:	TB Alliance	
	Protocol Number:	TBI-223-CL-001	
STATISTICAL ANALYSIS PLAN – PHASE 1			

Table Number	Table Title	Validation Method	Shell Number (if repeat)
14.3.7.10	12-Lead ECG Data, Overall Interpretation – Safety Analysis Set	IP	
14.3.8	Concomitant Medication		
	Not Applicable		
14.4	PK Tables		
14.4.1	Descriptive Statistics for Concentration-Time Data of TBI-223 and TBI-223 M2 after Single Doses of TBI-223 (Part 1; Cohorts 1-7)	MR	
14.4.2	Descriptive Statistics for Concentration-Time Data of TBI-223 and TBI-223 M2 after Single Doses of TBI-223 Oral Suspension (Part 1; Cohorts 1-7) by Gender		

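### The planned ECG and neurological tables do not show how many distinct subjects crossed a QTcF limit or had any abnormal post-dose neurological examination

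*SAP*

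**What the plan says.** **Neurological examination.** SAP 6.12.7 plans shift tables of the examination results: "each neurological aspect (Normal, Abnormal NCS, and Abnormal CS) will be tabulated by study part, period (where applicable) and treatment group at each post-baseline assessment". SAP 9 has one such table, 14.3.6.3.

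**ECG.** Under SAP 6.12.4, observed values and changes for the intervals, QTcF included, are "tabulated by study part, period (where applicable) and treatment group at each post-baseline assessment". SAP 6.3 fixes the statistics: "continuous variables will be summarized by the number of non-missing observations, mean, median, standard deviation, and minimum and maximum". The only categorical ECG display is a shift in overall interpretation, "from baseline to each post-baseline assessment will be presented. All ECG data, including details of any abnormalities, will be listed". SAP 9 lists two ECG tables: 14.3.7.9, titled "12-Lead ECG Data, Descriptive Statistics – Safety Analysis Set", and 14.3.7.10 for overall interpretation.

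**Repeat values.** SAP 6.2.8 states: "Only scheduled post-baseline assessments will be tabulated". Post-baseline repeats and unscheduled results appear only in listings.

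**What the protocol counts.** Rule 3 of Protocol 3.2 reads "Two or more subjects develop drug-related QTcF prolongation greater than or equal to 500 msec or a change from baseline greater than 60 msec", and applies once repeat testing is complete. Rule 2 counts subjects with drug-related CNS adverse events of grade 2 or above.

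**The concern.** Protocol 1.4 names QTc prolongation and tremor as the nonclinical findings behind its extra monitoring, and safety is the primary objective (SAP 2.1). A reader of the final report will want to know, for each dose and for placebo, how many subjects crossed a QTcF limit and how many had any abnormal neurological finding after dosing.

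Rows for different assessments cannot be added to get this, because one subject can appear in several. For QTcF there is not even a count at a single time point. Protocol 6.9.7 says that the ECG analysis will concentrate on QT and leaves the details to the SAP, but the SAP tabulates none of the protocol's QTcF limits.

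**Working it through.** The documents give no figure for this point, so there is nothing to reproduce. The check is what the planned tables can and cannot determine.

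**Inputs**
- Group size: 6 active per Part 1 cohort and 6 per Part 2 arm; 8 active in the food-effect cohort (SAP 1 and 4).
- Post-dose neurological examinations in Part 2: 3 h and 48 h (Protocol Appendix 6).
- Aspects per neurological examination: 7 (Protocol 6.9.5).
- QTcF limits: 500 msec absolute, and a change above 60 msec (Protocol 3.2, 1.4, Tables 9 and 16).

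**Step 1: neurological status.** Let c_t be the number of abnormal entries at assessment t in a group of n. The number D of distinct subjects ever abnormal satisfies max(c_t) ≤ D ≤ min(n, Σc_t).

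| Pattern | n | Lower bound | Upper bound |
|---|---|---|---|
| All rows zero | 6 | 0 | 0 |
| One abnormal at one time only | 6 | 1 | 1 |
| One at 3 h, one at 48 h | 6 | max(1,1) = 1 (1/6 = 17%) | min(6,2) = 2 (2/6 = 33%) |
| One at 3 h, one at 48 h | 8 | 1 (12.5%) | 2 (25%) |
| One in each of 7 aspects at one examination | 6 | 1 | min(6,7) = 6 |

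The tables fix D in special cases only. The last row shows that worst status per aspect is not enough by itself: an any-aspect row is needed too.

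**Step 2: QTcF.** Take invented changes at one time point of 65 msec in one subject and 0 in the other five.
- Mean = 65/6 = 10.8.
- SD = √(65²/6) = 26.5.
- Maximum = 65.

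If two time points both look like this, the table is identical whether one subject crossed 60 msec twice or two subjects crossed once. The maximum shows whether at least one scheduled value crossed. In general it does not show how many did.

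**Step 3: repeat values.** Rule 3 applies after repeat testing, and Tables 9 and 16 call for additional ECGs after a confirmed crossing. SAP 6.2.8 keeps repeat and unscheduled readings out of the tables, so confirmed and unconfirmed crossings cannot be told apart there.

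**Step 4: adverse event tables.** SAP 6.12.1 counts subjects by preferred term with maximum grade and, separately, by relationship. Under Protocol 1.4, ECG abnormalities become adverse events when clinically significant. A finding rated not clinically significant, or a numeric crossing not reported as an event, is not counted in these tables. No planned table crosses relationship with grade.

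**Step 5: the limits.** Protocol 3.2 uses 500 msec or more. Protocol 1.4, Table 9 (footnote e) and Table 16 (footnote d) use above 500 msec. Protocol 6.9.6 says that safety-ECG intervals are not noted unless part of an adverse event, while Protocol 1.4 has them noted on the CRF.

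**The case against.** The strongest reply is that this is a display gap in small groups. Every ECG and neurological value is listed (Listings 16.2.8.10 and 16.2.8.11), ordered by treatment and subject under SAP 6.3, and with about six active subjects per group the count can be made by hand. A per-time maximum below the limit already shows that no scheduled value crossed. All of this stands, and it limits the weight of the point. It does not supply a prespecified summary by treatment and placebo.

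Four stronger readings are tempting, and the documents do not support them.
- A reader might infer that the stopping rules cannot be applied. Protocol 3.1 and 3.2 place those decisions with the sponsor and investigator on live data, not with final SAP tables. Rule 3 also requires drug-relatedness, so a QTcF count would not reproduce it.
- A reader might infer that rule 2 is affected by how examinations are tabulated. It counts adverse events, not examination status, and the subject-level adverse event tables partly cover it.
- A reader might add a 72 h examination and widen the range to 1 to 3 of 6 (50%). Protocol 6.8 does list a neurological examination on Day 4, but Appendix 6 gives only 3 h and 48 h for Part 2. The firm range is 1 to 2.
- A reader might argue from effects clustering at peak concentration. Protocol 1.3 says it is unclear whether the nervous system effects follow Cmax or AUC. The point does not need that premise.

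The central ECG laboratory may have its own analysis plan. None is among the documents reviewed, and SAP 6.12.5 covers only the listing of Holter collection data.

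**Conclusion.** The point holds as a gap in reporting the primary safety objective. The planned tables do not give the number of distinct subjects per treatment beyond the protocol's QTcF limits, or with any post-dose neurological abnormality, except in special cases such as all-zero rows. In the simplest ambiguous case the uncertainty is 1 versus 2 of 6 subjects. For QTcF the count at a single time point is missing as well. No data are lost and live safety decisions are not affected.

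This rests on the SAP's table list being complete, on no separate cardiodynamic plan supplying the QTcF count, and on QTcF being recorded for the safety ECGs, as SAP 6.12.4 presupposes. The 65 msec example is illustrative only.

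**What to change.** 1. **Reconcile first.** Align Protocol 3.2 with Protocol 1.4 and the footnotes to Tables 9 and 16 on whether exactly 500 msec counts. Align Protocol 6.9.6 with 1.4 on whether safety-ECG intervals are recorded.
2. **SAP 6.12.4 and Table 14.3.7.9.** Add, by treatment (placebo included) and period, the number of subjects with any post-dose QTcF beyond the reconciled absolute limit, and the number with any change from baseline above 60 msec. Include repeat and unscheduled values, and show separately the subjects confirmed on repeat testing. For this a repeat has to stay separate from the first reading, not be averaged with it under SAP 6.2.7.
3. **SAP 6.12.7 and Table 14.3.6.3.** Add a shift from baseline to worst post-dose status for each aspect, plus one overall any-aspect row, counting each subject once per dosing period.
4. **SAP 6.2.8.** State that these subject-level counts are an exception to the scheduled-only rule.

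The cost is a few derived flags and table rows, from values that the SAP already plans to tabulate or list, plus clarification of the protocol passages in item 1. No new assessments are needed.

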7 CHANGES TO PLANNED PROTOCOL ANALYSIS

No changes to the planned analyses have been identified.

QMD Ref: Worldwide-TMP-ST-006-4.0 Effective: 12Aug2019	Governing QMD: Worldwide-SOP-ST-001
Confidentiality Statement	

This document is the property of Worldwide Clinical Trials Inc. and may not be duplicated, copied, altered or removed from company without prior approval from Worldwide Quality Assurance or in compliance with Worldwide Standard Operating Procedures.

Worldwide Clinical Trials Controlled Quality Management Document			
 WORLDWIDE CLINICAL TRIALS	Sponsor:	TB Alliance	
	Protocol Number:	TBI-223-CL-001	
STATISTICAL ANALYSIS PLAN – PHASE 1			

9 LIST OF TABLES, FIGURES AND LISTINGS

The following table includes details of the tables, figures and listings to be included within each section of the eCTD. The eCTD section is shown in bold. The following validation methods maybe used:

- Independent programming of numbers and manual review of format (IP)
- Independent programming by statistician of numbers and manual review of format (Stat IP)
- Manual review (MR)
- Code review (CR)

Please note, PK Table, Figure and Listing numbers and titles are subject to change and may be consolidated upon final analysis.

Table Number	Table Title	Validation Method	Shell Number (if repeat)
Items in bold are not table titles but references to the section headings within eCTD.			
14.1	Demographics Data		
14.1.1	Disposition		
14.1.1.1	Subject Disposition, Early Withdrawals - All Enrolled Subjects	IP	
14.1.2	Demographics		
14.1.2.1	Demographics - Safety Analysis Set	IP	
14.1.3	Baseline Characteristics		
	Not Applicable		
14.2	Efficacy Data		
	Not Applicable		
14.3	Safety Data		
14.3.1	Displays of Adverse Events		
14.3.1.1	Adverse Events, Overall Summary of Treatment-Emergent Adverse Events (TEAEs) – Safety Analysis Set	IP	
14.3.1.2	Adverse Events, TEAEs by Primary System Organ Class and Preferred Term – Safety Analysis Set	IP	
14.3.1.3	Adverse Events, Treatment-Related TEAEs by Primary System Organ Class and Preferred Term – Safety Analysis Set	IP	
14.3.1.4	Adverse Events, TEAEs by Primary System Organ Class, Preferred Term and Maximum Grade – Safety Analysis Set	IP	

QMD Ref: Worldwide-TMP-ST-006-4.0 Effective: 12Aug2019	Governing QMD: Worldwide-SOP-ST-001
Confidentiality Statement	

This document is the property of Worldwide Clinical Trials Inc. and may not be duplicated, copied, altered or removed from company without prior approval from Worldwide Quality Assurance or in compliance with Worldwide Standard Operating Procedures.

Worldwide Clinical Trials Controlled Quality Management Document			
 WORLDWIDE CLINICAL TRIALS	Sponsor:	TB Alliance	
	Protocol Number:	TBI-223-CL-001	
STATISTICAL ANALYSIS PLAN – PHASE 1			

Table Number	Table Title	Validation Method	Shell Number (if repeat)
14.3.1.5	Adverse Events, TEAEs by Primary System Organ Class, Preferred Term and Nearest Relationship – Safety Analysis Set	IP	
14.3.2	Listings of Deaths, Other Serious and Significant Adverse Events		
14.3.2.1	TEAEs Leading to Early Withdrawal, Listing – Safety Analysis Set	IP	
14.3.2.2	Serious TEAEs, Listing – Safety Analysis Set	IP	
14.3.2.3	Deaths, Listing – Safety Analysis Set	IP	
14.3.3	Narratives of Deaths, Other Serious and Certain Other Significant Adverse Events		
14.3.4	Abnormal Laboratory Values		
14.3.4.1	Listing of Clinically Significant Laboratory Values – Safety Analysis Set	IP	
14.3.5	Extent of Exposure, Dosage Information, and Compliance		
	Not Applicable		
14.3.6	Vital Signs and Physical Examination		
14.3.6.1	Vital Signs, Descriptive Statistics – Safety Analysis Set	IP	
14.3.6.2	Physical Examination, Change from Baseline – Safety Analysis Set	IP	
14.3.6.3	Neurological Examination, Change from Baseline – Safety Analysis Set	IP	
14.3.7	Other Safety		
14.3.7.1	Hematology Data, Descriptive Statistics – Safety Analysis Set	IP	
14.3.7.2	Hematology Data, Normal Range Shifts – Safety Analysis Set	IP	
14.3.7.3	Serum Chemistry Data, Descriptive Statistics – Safety Analysis Set	IP	
14.3.7.4	Serum Chemistry Data, Normal Range Shifts – Safety Analysis Set	IP	
14.3.7.5	Coagulation Data, Descriptive Statistics – Safety Analysis Set	IP	
14.3.7.6	Coagulation Data, Normal Range Shifts – Safety Analysis Set	IP	
14.3.7.7	Urinalysis Data, Descriptive Statistics – Safety Analysis Set	IP	
14.3.7.8	Urinalysis Data, Normal Range Shifts – Safety Analysis Set	IP	
14.3.7.9	12-Lead ECG Data, Descriptive Statistics – Safety Analysis Set	IP	

QMD Ref: Worldwide-TMP-ST-006-4.0 Effective: 12Aug2019	Governing QMD: Worldwide-SOP-ST-001
Confidentiality Statement	
This document is the property of Worldwide Clinical Trials Inc. and may not be duplicated, copied, altered or removed from company without prior approval from Worldwide Quality Assurance or in compliance with Worldwide Standard Operating Procedures.	

Worldwide Clinical Trials Controlled Quality Management Document			
 WORLDWIDE CLINICAL TRIALS	Sponsor:	TB Alliance	
	Protocol Number:	TBI-223-CL-001	
STATISTICAL ANALYSIS PLAN – PHASE 1			

Table Number	Table Title	Validation Method	Shell Number (if repeat)
14.3.7.10	12-Lead ECG Data, Overall Interpretation – Safety Analysis Set	IP	
14.3.8	Concomitant Medication		
	Not Applicable		
14.4	PK Tables		
14.4.1	Descriptive Statistics for Concentration-Time Data of TBI-223 and TBI-223 M2 after Single Doses of TBI-223 (Part 1; Cohorts 1-7)	MR	
14.4.2	Descriptive Statistics for Concentration-Time Data of TBI-223 and TBI-223 M2 after Single Doses of TBI-223 Oral Suspension (Part 1; Cohorts 1-7) by Gender		
14.4.3	Descriptive Statistics for Concentration-Time Data of TBI-223 and TBI-223 M2 after Single Doses of TBI-223 (Part 2; Cohorts 8 and 9)	MR	
14.4.4	Descriptive Statistics for Concentration-Time Data of TBI-223 and TBI-223 M2 after Single Doses of TBI-223 (Part 2; Cohorts 8 and 9) by Gender	MR	
14.4.5	Plasma Pharmacokinetic Parameters of TBI-223 after Single Doses of TBI-223 (Part 1; Cohorts 1-7)	MR	
14.4.6	Plasma Pharmacokinetic Parameters of TBI-223 after Single Doses of TBI-223 (Part 1; Cohorts 1-7) by Gender		
14.4.7	Plasma Pharmacokinetic Parameters of TBI-223 M2 after Single Doses of TBI-223 (Part 1; Cohorts 1-7)		
14.4.8	Plasma Pharmacokinetic Parameters of TBI-223 M2 after Single Doses of TBI-223 (Part 1; Cohorts 1-7) by Gender		
14.4.9	Plasma Pharmacokinetic Parameters of TBI-223 after Single Doses of TBI-223 (Part 2; Cohorts 8 and 9)		
14.4.10	Plasma Pharmacokinetic Parameters of TBI-223 after Single Doses of TBI-223 (Part 2; Cohorts 8 and 9) by Gender		
14.4.11	Plasma Pharmacokinetic Parameters of TBI-223 M2 after Single Doses of TBI-223 (Part 2; Cohorts 8 and 9)		
14.4.12	Plasma Pharmacokinetic Parameters of TBI-223 M2 after Single Doses of TBI-223 (Part 2; Cohorts 8 and 9) by Gender		

QMD Ref: Worldwide-TMP-ST-006-4.0 Effective: 12Aug2019	Governing QMD: Worldwide-SOP-ST-001
Confidentiality Statement	

This document is the property of Worldwide Clinical Trials Inc. and may not be duplicated, copied, altered or removed from company without prior approval from Worldwide Quality Assurance or in compliance with Worldwide Standard Operating Procedures.

Worldwide Clinical Trials Controlled Quality Management Document			
 WORLDWIDE CLINICAL TRIALS	Sponsor:	TB Alliance	
	Protocol Number:	TBI-223-CL-001	
STATISTICAL ANALYSIS PLAN – PHASE 1			

Table Number	Table Title	Validation Method	Shell Number (if repeat)
14.4.13	Assessment of Dose Proportionality Following Single-Dose Administrations of TBI-223 under Fasted Conditions (Part 1; Cohorts 1-7)	MR	
14.4.14	Statistical Analysis of the Natural Log-Transformed- Systemic Exposure of TBI-223 after a Single 1200 mg Dose of TBI-223 Oral Suspension under Fed (Test) and Fasted (Reference) Conditions (Part 1; Cohort 5)	MR	
14.4.15	Statistical Analysis of the Natural Log-Transformed- Systemic Exposure of TBI-223 after a Single 300 mg Dose of TBI-223 Capsule Formulation (Cohort 3 Repeat; Part 1) and a Single 300 mg Dose of TBI-223 Oral Suspension (Cohort 3; Part 1)		
14.4.16	Statistical Analysis of the Natural Log-Transformed- Systemic Exposure of IR, 2000 mg (2 x 1000 mg TBI-223 tablets) under Fed Conditions (Cohort 9) and IR, 2000 mg (2 x 1000 mg TBI-223 tablets) under Fasted Conditions (Cohort 8)	MR	
14.4.17	Statistical Analysis of the Natural Log-Transformed- Systemic Exposure of SR (Prototypes 1, 2, and 3), 1800 mg (2 x 900 mg TBI-223 tablets) under Fed Conditions (Cohort 8) and IR, 2000 mg (2 x 1000 mg TBI-223 tablets) under Fasted Conditions (Cohort 8)	MR	
14.4.18	Statistical Analysis of the Natural Log-Transformed- Systemic Exposure of SR (Prototypes 1, 2, and 3), 1800 mg (2 x 900 mg TBI-223 tablets) under Fed Conditions (Cohort 8) and IR, 2000 mg (2 x 1000 mg TBI-223 tablets) under Fed Conditions (Cohort 9)	MR	

QMD Ref: Worldwide-TMP-ST-006-4.0 Effective: 12Aug2019	Governing QMD: Worldwide-SOP-ST-001
Confidentiality Statement	
This document is the property of Worldwide Clinical Trials Inc. and may not be duplicated, copied, altered or removed from company without prior approval from Worldwide Quality Assurance or in compliance with Worldwide Standard Operating Procedures.	

Worldwide Clinical Trials Controlled Quality Management Document			
 WORLDWIDE CLINICAL TRIALS	Sponsor:	TB Alliance	
	Protocol Number:	TBI-223-CL-001	
STATISTICAL ANALYSIS PLAN – PHASE 1			

Figure Number	Figure Title		
14.4.1	Mean Plasma Concentration-Time Profiles of TBI-223 and TBI-223 M2 after Single Doses of TBI-223 Administered under Fasted Conditions (Part 1; Cohorts 1-7) on Linear and Semi Logarithmic Scales	MR	
14.4.2	Mean Plasma Concentration-Time Profiles of TBI-223 and TBI-223 M2 after a Single 1200 mg Dose of TBI-223 Oral Suspension under Fed and Fasted Conditions (Part 1; Cohort 5) on Linear and Semi Logarithmic Scales	MR	
14.4.3	Mean Plasma Concentration-Time Profiles of TBI-223 and TBI-223 M2 after a Single 300 mg Dose of TBI-223 Oral Suspension (Cohort 3; Part 1) and a Single 300 mg Dose of TBI-223 Capsule Formulation (Cohort 3 Repeat; Part 1) on Linear and Semi Logarithmic Scales	MR	
14.4.4	Mean Plasma Concentration-Time Profiles of TBI-223 and TBI-223 M2 after Single Doses of TBI-223 (Cohorts 8, and 9; Part 2) on Linear and Semi Logarithmic Scales	MR	
14.4.5	Mean Plasma Concentration-Time Profiles of TBI-223 and TBI-223 M2 for Males and Females by Cohort (Part 1) on Linear and Semi Logarithmic Scales		
14.4.6	Mean Plasma Concentration-Time Profiles of TBI-223 and TBI-223 M2 for Males and Females by Cohort (Part 2) on Linear and Semi Logarithmic Scales		
14.4.7	All Subject Plasma Concentration-Time Profiles of TBI-223 and TBI-223 M2 after Single Doses of TBI-223 (Cohorts 1-7; Part 1) on Linear and Semi Logarithmic Scales	MR	
14.4.8	All Subject Plasma Concentration-Time Profiles of TBI-223 and TBI-223 M2 after Single Doses of TBI-223 (Cohorts 8 and 9; Part 2) on Linear and Semi Logarithmic Scales	MR	
14.4.9	Individual Plasma Concentration-Time Profiles of TBI-223 and TBI-223 M1 after a Single 1200 mg Dose of TBI-223 Oral Suspension under Fed and Fasted Conditions (Part 1, Cohort 5) on Linear and Semi Logarithmic Scales	MR	
14.4.10	Individual Plasma Concentration-Time Profiles of TBI-223 and TBI-223 M2 after a Single Dose of TBI-223 Oral Suspension (Cohort 3; Part 1) and a Single Dose of	MR	

QMD Ref: Worldwide-TMP-ST-006-4.0 Effective: 12Aug2019	Governing QMD: Worldwide-SOP-ST-001
Confidentiality Statement	

This document is the property of Worldwide Clinical Trials Inc. and may not be duplicated, copied, altered or removed from company without prior approval from Worldwide Quality Assurance or in compliance with Worldwide Standard Operating Procedures.

Worldwide Clinical Trials Controlled Quality Management Document			
 WORLDWIDE CLINICAL TRIALS	Sponsor:	TB Alliance	
	Protocol Number:	TBI-223-CL-001	
STATISTICAL ANALYSIS PLAN – PHASE 1			

Figure Number	Figure Title		
	TBI-223 Capsule Formulation (Cohort 3 Repeat; Part 1) on Linear and Semi Logarithmic Scales		
14.4.11	Concentration-Time Profiles for TBI-223 and TBI-223 M2 with Linear Regression for Estimating the Terminal Elimination Rate	MR	

QMD Ref: Worldwide-TMP-ST-006-4.0 Effective: 12Aug2019	Governing QMD: Worldwide-SOP-ST-001
Confidentiality Statement	
This document is the property of Worldwide Clinical Trials Inc. and may not be duplicated, copied, altered or removed from company without prior approval from Worldwide Quality Assurance or in compliance with Worldwide Standard Operating Procedures.	

Worldwide Clinical Trials Controlled Quality Management Document			
 WORLDWIDE CLINICAL TRIALS	Sponsor:	TB Alliance	
	Protocol Number:	TBI-223-CL-001	
STATISTICAL ANALYSIS PLAN – PHASE 1			

Listing Number	Listing Title	Validation Method	Shell Number (if repeat)
16.2	Subject Data Listings		
16.2.1	Discontinued Subjects		
16.2.1.1	Subject Disposition - All Enrolled Subjects	IP	
16.2.2	Protocol Deviations		
16.2.2.1	Protocol Deviations – Safety Analysis Set	IP	
16.2.3	Subjects Excluded from The Efficacy Analyses		
16.2.3.1	Analysis Sets - All Enrolled Subjects	IP	
16.2.4	Demographic Data		
16.2.4.1	Demographic Data – Safety Analysis Set	IP	
16.2.4.2	Previous and Ongoing Medical History – Safety Analysis Set	IP	
16.2.5	Compliance and/or Drug Concentration Data		
16.2.5.1	PK Sampling Data – Safety Analysis Set	IP	
16.2.5.2	Dosing Information – Safety Analysis Set	IP	
16.2.5.3	Prior and Concomitant Medication – Safety Analysis Set	IP	
16.2.6	Individual Efficacy Response Data		
16.2.6.1	Plasma TBI-223 and TBI-223 M2 Concentration Listing by Subject (Part 1)	MR	
16.2.6.2	Plasma TBI-223 and TBI-223 M2 Concentration Listing by Subject (Part 2)		
16.2.6.3	Terminal Elimination Rate of TBI-223 and TBI-223 M2 in Plasma for Individual Subjects (Part 1)	MR	
16.2.6.4	Terminal Elimination Rate of TBI-223 and TBI-223 M2 in Plasma for Individual Subjects (Part 2)		
16.2.6.5	PK Output for TBI-223 and TBI-223 M2	MR	
16.2.6.6	Statistical Analysis SAS Output for Dose Proportionality (Part 1)	MR	
16.2.6.7	Statistical Analysis SAS Output for Food Effect Assessment (Part 1, Cohort 5)	MR	
16.2.6.8	Statistical Analysis SAS Output for Formulation Effect Assessment (Part 1, Cohort 3 and Cohort 3 Repeat)	MR	
16.2.6.9	Statistical Analysis SAS Output for Food Effect Assessment (IR tablets; Part 2)	MR	
16.2.6.10	Statistical Analysis SAS Output (SR Fed vs. IR Fasted; Part 2)	MR	

QMD Ref: Worldwide-TMP-ST-006-4.0 Effective: 12Aug2019	Governing QMD: Worldwide-SOP-ST-001
Confidentiality Statement	
This document is the property of Worldwide Clinical Trials Inc. and may not be duplicated, copied, altered or removed from company without prior approval from Worldwide Quality Assurance or in compliance with Worldwide Standard Operating Procedures.	

Worldwide Clinical Trials Controlled Quality Management Document			
 WORLDWIDE CLINICAL TRIALS	Sponsor:	TB Alliance	
	Protocol Number:	TBI-223-CL-001	
STATISTICAL ANALYSIS PLAN – PHASE 1			

Listing Number	Listing Title	Validation Method	Shell Number (if repeat)
16.2.6.11	Statistical Analysis SAS Output (SR Fed vs IR Fed; Part 2)	MR	
16.2.7	Adverse Event Listings		
16.2.7.1	Adverse Event Data – Safety Analysis Set	IP	
16.2.8	Individual Laboratory Measurement and Other Safety		
16.2.8.1	Hematology Data – Safety Analysis Set	IP	
16.2.8.2	Serum Chemistry Data – Safety Analysis Set	IP	
16.2.8.3	Coagulation Data – Safety Analysis Set	IP	
16.2.8.4	Urinalysis Data – Safety Analysis Set	IP	
16.2.8.5	Drug and Alcohol Screening Data – Safety Analysis Set	IP	
16.2.8.6	Serology Data – Safety Analysis Set	IP	
16.2.8.7	Pregnancy Test Data – Safety Analysis Set	IP	
16.2.8.8	Vital Signs Data – Safety Analysis Set	IP	
16.2.8.9	Physical Examination Data – Safety Analysis Set	IP	
16.2.8.10	Neurological Examination Data – Safety Analysis Set	IP	
16.2.8.11	12-Lead ECG Data – Safety Analysis Set	IP	
16.2.8.12	Cardiac Telemetry (Holter) Collection Data – Safety Analysis Set	IP	
16.2.8.13	Breath Strip Application Data – Safety Analysis Set	IP	

QMD Ref: Worldwide-TMP-ST-006-4.0 Effective: 12Aug2019	Governing QMD: Worldwide-SOP-ST-001
Confidentiality Statement	
This document is the property of Worldwide Clinical Trials Inc. and may not be duplicated, copied, altered or removed from company without prior approval from Worldwide Quality Assurance or in compliance with Worldwide Standard Operating Procedures.
